C.5.2.5. Subjective Insomnia Severity Measures. Subjective insomnia severity will be evaluated utilizing the *Insomnia Severity Index* (Bastien, Vallieres, & Morin, 2001). The ISI provides a global measure of perceived insomnia severity. The total scores range from 0-28, with higher scores indicating higher severity. The ISI has excellent internal consistency (Cronbach alpha = 0.74) and temporal stability ($r = 0.80$). The ISI has been validated with sleep diaries and PSG (Bastien, Vallieres, & Morin, 2001). In clinical samples, a cut off score of 11 was shown to have the greatest sensitivity and specificity for correctly identifying study participants meeting criteria for insomnia diagnosis (Morin, Belleville, Belanger, & Ivers, 2011). Because we are using the ISI as a screening measure and as a within-subject outcome, we will use a cut score of 8, which is indicative of subthreshold insomnia. Diagnosis of insomnia will be determined by a structured sleep interview. Other sleep measures to be used, each of which has been shown to have internal consistency and validity, include the *Pittsburgh Sleep Quality Index* (PSQI; Buysse, Reynolds, Monk, Berman, & Kupfer, 1989), a 19-item measure of sleep quality and disturbances over the past month, the *Pittsburgh Sleep Quality Index-Addendum* (PSQI-A; Germain, Hall, Krakow, Katherine, & Buysse, 2005), which assesses other disruptive nocturnal behaviors related to PTSD including hot flashes, nightmares and episodes of terror during sleep; and the *Epworth Sleepiness Scale* (ESS; Johns, 1991), an 8-item measure of perceived daytime sleepiness.

C.5.2.6. Sleep-Related Arousal. The Pre-Sleep Arousal Scale (PSAS; Jansson-Frömmark & Norell-Clarke, 2012) is a widely used measure of pre-sleep arousal with cognitive and somatic arousal subscales.

Scores on the 13-item measure range from 8-40. The PSAS demonstrated acceptable internal consistency on both the cognitive and somatic arousal subscales, and it effectively discriminated between normal sleepers, poor sleepers, and those with insomnia disorder. The PSAS demonstrated convergent validity with measures of sleep-related worry, sleep-related beliefs, anxiety, depression, sleep parameters, and daytime impairment.

C.5.3. Demographic Variables, Medical Screen and Health Risk Behaviors. Each participant's medical history will be reviewed, and clinic BP will be determined by standard sphygmomanometry. We will collect demographic, health risk, and other clinical information that will be used in part to characterize study participants' 10-year risk for ASCVD (Goff et al., 2013). Education, occupation and household income will be added to provide a composite measure. Education will be measured by highest degree earned. Occupation will be coded into three categories. This summary variable has been reported in studies examining the relationship between social status and psychological and physiological functioning (Adler, Epel, Castellazzo, & Ickovics, 2000). We will collect information about participants' current medications and current/lifetime medical diagnoses. In addition, we will collect data on body mass index (BMI), calculated using participant's weight and height. This measurement will be done at the baseline lab visit. The *Fagerström Test of Nicotine Dependence* (FTND; Heatherton, Kozlowski, Frecker, & Fagerström, 1991) and a smoking history questionnaire (e.g., number of cigarettes smoked/day, age of first smoking, number of previous quit attempts) will be used to measure smoking behaviors. Self-reported alcohol use will be assessed with the three-item AUDIT-C (Bush, Kivlahan, McDonnel, Fihn, & Bradley, 1998), which has demonstrated reliability and validity (Crawford et al., 2013). The Leisure Time Exercise Questionnaire (Godin & Shephard, 1985) will be collected *via* Qualtrics during the day of ABP assessment. We will also check for the presence of cognitive impairment using the *Montreal Cognitive Assessment* (MoCA; Nasreddine et al., 2005). This tool has been used as a short cognitive screening tool for identifying impaired cognitive functioning in the general population; scores range from 0 to 30, and any individual who scores below 20 will be excluded from participation due to the presence of cognitive impairment (Gallagher et al., 2013). Although the cut score of 26 has good specificity and sensitivity to diagnose mild cognitive impairment (MCI; Hoops et al., 2009), we do not wish to rule out participants with MCI, but rather those with dementia. A cut score of 26 will likely otherwise suitable participants, as CPT has been successfully used in patients with traumatic brain injury (TBI) and MCI. Any participant who is excluded due to low MoCA scores will be informed of the results and encouraged to discuss the findings with their personal physician or care provider for further evaluation and treatment if necessary.

C.5.4. Measurement of Other Potential Covariates. Menopausal status will be documented by self-reported menstrual bleeding, using the criteria described by Tom and colleagues (2010). Status categories are postmenopausal (natural or surgical), perimenopausal, and premenopausal. Menopausal status and lifetime alcohol use disorder (as well as current alcohol consumption measured as drinks per week) will be considered as potential covariates in analytic models. Pain will be measured with the 3-item PEG, a reliable and valid brief version of the Brief Pain Inventory (Krebs et al., 2009). For descriptive and analytic purposes, each patient's medications will be recorded and classified as: anticholinergic; alpha-adrenergic blockade; beta-blockade and other anti-hypertensive medications (diuretics, ACE inhibitors, and calcium channel blockers); specific serotonin re-uptake inhibitor (SSRI);

heterocyclic antidepressant; lithium; MAOI anti-depressant; other antidepressant; neuroleptic; or sedative-hypnotic. This classification system is based on our previous work involving the input and consensus of our team physicians ([name] et al., 2000).

C.6. Measures of Cardiovascular Disease Risk

C.6.1. Assessment of 24-hour Ambulatory Blood Pressure (ABP). We have experience measuring 24-hour ABP and will use the Oscar 2 ABP monitor (Suntech Medical Inc., Raleigh, NC), which has been validated by previous investigators (Goodwin, Bilous, Winship, Finn, & Jones, 2007; Jones, Bilous, Winship, Finn, & Goodwin, 2004). Clinic BP will be determined according to the new ACC/AHA guidelines (Whelton et al., 2018) with three readings taken after five minutes of quiet rest in a seated posture, each separated by 2 minutes, using the Oscar 2 BP monitor together with appropriate cuff size, and averaged to represent clinic BP. Subsequently, the ABP monitor will be programmed to take BP measurements every 20 minutes throughout the waking hours and every 30 minutes during the nighttime sleep period. We have used this procedure with excellent participant acceptability and compliance in numerous previous studies (Blumenthal, [name], & Gullette, 2000; Carels, [name], Szczepanski, & Blumenthal, 2000; Prather, Blumenthal, Hinderliter, & [name], 2011; [name] et al., 2011; [name], Thurston, Steffen, Blumenthal, Waugh, & Hinderliter, 2001). A successful 24-hour study will require at least 80% of the total readings to be valid, with no more than two consecutive hours lacking a valid reading (White et al., 2006). Unsuccessful ABP studies will be repeated.

In addition to mean 24-hour ABP, mean waking and nighttime ABP will be computed, with the nighttime sleep period defined by self-report and confirmed by actigraphy ([name] et al., 2001; [name] et al., 2011; [name] et al., 2002). Nighttime BP dipping will be defined as the percentage of the decline in nighttime systolic blood pressure (SBP) [(mean daytime SBP- mean nighttime SBP/mean daytime SBP) \times 100]; SBP dipping defined in this way is a continuous variable that will be a primary outcome measure in this proposed RCT. In addition, for descriptive purposes, a SBP dip \geq 10% will be classified as normal “dipper”, while $<10\%$ will be classified as “non-dipper”, with secondary analyses evaluating intervention effects on dipping status. Twenty-four-hour ABP assessments will be obtained at pre-randomization baseline, upon completion of the 8-week intervention, and at 6-month follow-up, in order to evaluate intervention effects on ABP and nighttime BP dipping.

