In an innovative use of an established and well validated intervention for insomnia, we propose to examine the direct effects of sleep on biomarkers of CVD risk outcomes among persons with PTSD and comorbid insomnia disorder (ID; see Figure 1). In this 2-arm RCT, 150 participants with PTSD and ID will be randomized at a 2:1 ratio to either CBT-I, or a minimal contact control condition (CCC). We anticipate that we may need to consent and screen as many as 500 participants to reach this goal. Sleep efficiency as measured by actigraphy will be the primary sleep outcome measure. Other parameters [total sleep time (TST) wake after sleep onset (WASO), sleep fragmentation] will be measured with a multi-modal assessment strategy including validated self-report measures, sleep diaries collected *via* Qualtrics, and objective sleep measurement (i.e., actigraphy). Sleep diaries and actigraphy will be continuously collected for 10-weeks (including a week-long baseline, 8-week period for CBT-I or CCC, and one-week post treatment) and for a week-long period at the 6-month follow-up. The primary outcomes for this clinical trial are established biomarkers of CVD risk, including flow mediated dilation, SNS activity, nighttime BP, nighttime BP dipping, and ASCVD risk. These biomarkers will be assessed at three time points: baseline, post-intervention (8-weeks), and 6-month follow-up. The 6-month follow-up period will allow us to evaluate whether the intervention effects on CVD risk are sustained beyond the immediate post-intervention period. Timing for the 6-month follow-up visit will be 6 months after

the baseline assessment or three months after the post-intervention assessment, whichever is later. Participants in both arms will continue with usual medical care.

C.2. Recruitment

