Participants must meet each of the following inclusion criteria:

- Are between 40-59 years old;
- Has a current diagnosis of chronic PTSD (at least 3 months duration) based on the Clinician Administered PTSD Scale DSM-5 version (Weathers et al., 2013);
- Has a current diagnosis of ID as defined in the International Classification of Sleep Disorders

(ICSD-3; American Academy of Sleep Medicine, 2014)

Participants who meet any of the following criteria will be excluded from participation:

- Has a history of CVD events, including myocardial infarction, stroke, transient ischemic attack, or coronary revascularization;
- Has diagnosis of congestive heart failure or coronary artery disease based on results of diagnostic testing;
- Has a current alcohol use or substance use disorder (those who meet lifetime but not current alcohol or substance use disorder will be included);
- Is currently participating in an evidence-based trauma focused therapy for PTSD (i.e., Prolonged Exposure, Cognitive Processing Therapy, or Eye Movement Desensitization and Reprocessing);
- Has cognitive impairment as evidenced by less than 20 on the Montreal Cognitive Assessment scale (MOCA; Nasreddine et al., 2005);
- Meets criteria for a psychotic spectrum disorder or bipolar disorder;
- Has severely impaired hearing or speech;
- Is pregnant;
- Does not use benzodiazepines for sleep, and if prescribed benzodiazepines for some other use (e.g., anxiety, panic attacks), uses them fewer than four times in a one month period.;
- Is not stable (medications and dose stable for one month) on any other current psychoactive and/or cardiovascular medications or will not be stable on these medications during the course of the study;
- Works night shift;
- Is participating in another interventional study to address insomnia;
- Has prominent suicidal or homicidal ideation (as assessed through a clinical interview);
- Has nonclinically significant or sub-threshold insomnia as indicated by a score of <8 on the Insomnia Severity Index;
- Has seizures (based on clinical interview and self-report);
- Has a body mass index of 45 or greater;
- Has sleep apnea (based on the overnight assessment described below) or a positive sleep apnea screen;

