During the study, study staff members will communicate with participants via phone, email, standard mail, or texts sent from a Duke-owned phone, based on participant preferences. Participants will be allowed to opt out of texting or emailing if they wish.

C.4. Interventions

C.4.1. Cognitive Behavior Therapy for Insomnia (CBT-I). The approach to CBT-I for the proposed study is based on CBT-I programs that have been practiced and studied by research team members (Karlin, Trockel, Tylor, Gimeno, & Manber, 2013; Manber, Carney, & Edinger, 2012). CBT-I is manualized in a session-by-session guide (Perlis, Jungquist, Smith, & Posner, 2005). [name] serves as a consultant and trainer on the nationwide dissemination of CBT-I. [name] will train study therapists to deliver CBT-I in accordance with the training approach adopted by the CBT-I dissemination effort (Karlin, Trockel, Tylor, Gimeno, & Manber, 2013). Further, [name] will be available for consultation regarding the training procedures and fidelity measures and methods.

C.4.2. Minimal Contact Control Condition. Participants assigned to the CCC will be contacted via WebEx or Zoom every week for eight weeks. To monitor their insomnia symptoms and mood, they will be asked to complete the PTSD Checklist and Insomnia Severity Index. Check-in calls will be audio-recorded. This will allow us to do fidelity ratings to ensure that participants are not receiving any sleep interventions, advice, etc. Please note that our lab has an SOP related to suicide risk assessment, and the study coordinator who makes the check-in calls has been trained in the use of the SOP. Participants

will be asked about any insomnia treatments they use/receive during usual care. At the end of the 6-month follow-up, participants randomized to this condition will be offered CBT-I.

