Everyday Discrimination Scale	Participant	X ¹			
Short Form-36 Health Survey	Participant		X	X	X
Daily sleep diaries	Participant	X	X	X	X
Insomnia Severity Index	Participant	X ¹	X	X	X
Pittsburgh Sleep Quality Index with PTSD addendum	Participant		X	X	X

Epworth Sleepiness Scale	Participant	X ¹			
Medical Problems Checklist	Study coordinator ¹	X ¹			
STOP-BANG	Participant	X ¹			
Pre-Sleep Arousal Scale	Participant		X	X	X
Demographics measure	Participant	X ¹			
Fagerström Test for Nicotine Dependence	Participant	X ¹			
AUDIT-C	Participant	X ¹			
Leisure Time Exercise Questionnaire	Participant		X	X	X
Menopausal status	Participant		X		X
PEG	Participant	X ¹			
Medications List	Participant	X ¹	X	X	X
Insomnia Treatment Measure	Participant			X	Xau
Over-the-Counter Medications List	Participant	X ¹	X	X	X
Physiological Measures					
Actigraphy	Study staff ²		X	X	X
WatchPAT One sleep apnea assessment	Participant	X ²			
24-hour blood pressure assessment	Study staff ²		X	X	X
Flow mediated dilation	Study staff ²		X	X	X
24-hour urinary catecholamines	Participant ²		X	X	X
ASCVD risk	Study staff ²		X	X	X
Body Mass Index	Study staff ²		X	X	X

* Superscript 1 indicates that these procedures are completed at the first screen visit, and superscript 2 items are completed at the second screen visit.

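### C.3 has no criterion for current or recent behavioural insomnia therapy in usual care, and no listed measure is described as recording it before randomisation

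*Combined protocol and SAP*

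**What the plan says.** The relevant text is in four places of the combined protocol and SAP.

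- **C.3, exclusions.** The bullet on other insomnia interventions is limited to research: "Is participating in another interventional study to address insomnia". The bullet on PTSD therapy has no such limit: "Is currently participating in an evidence-based trauma focused therapy for PTSD". Two further bullets touch on drug treatment. One begins "Does not use benzodiazepines for sleep", and the other is a stability rule: "Is not stable (medications and dose stable for one month) on any other current psychoactive and/or cardiovascular medications". The severity floor is: "Has nonclinically significant or sub-threshold insomnia as indicated by a score of <8 on the Insomnia Severity Index". A current insomnia disorder diagnosis is an inclusion criterion.
- **C.5, study measures table (headed Table 2).** The row "Insomnia Treatment Measure" is marked at post-treatment and 6 months. Its Screen and Baseline cells are empty. The medications list is marked at all four time points.
- **C.1.** "Participants in both arms will continue with usual medical care".
- **C.4.2 (control condition).** Participants "will be asked about any insomnia treatments they use/receive during usual care". This stands among the procedures that follow assignment.

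C.3 stratifies randomisation by gender and smoking. Prior or current behavioural insomnia treatment is not among the potential covariates in C.5.4 or the moderators in D.3.

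**The concern.** Aim 1 compares people given CBT-I with people not given it. D.3 tests this through treatment contrasts in change from baseline. Someone already in CBT-I at entry has a baseline week that is partly treated. If allocated to control, that person may go on receiving the active therapy; if allocated to CBT-I, the person repeats it. Someone who has just finished a course may carry its effect into baseline. B.5 itself describes the gains from CBT-I as long-lasting, and as maintained at 6 months in PTSD, so carry-over follows from the plan's own premise.

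Such people could present. C.2 recruits from primary care, PTSD clinics and the community, B.5 says that non-specialists can deliver CBT-I, and C.4.1 refers to a national roll-out. The plan already controls concurrent PTSD therapy and medication changes, yet leaves out clinical use of the therapy under test. At stake are a weaker contrast and the lack of a baseline variable with which to see how much weaker it is.

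**Working it through.** **Step 1: read the eligibility rule as written.** Take a person in the third week of CBT-I at a clinic, with current insomnia disorder and an ISI of 8 or more.

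| C.3 criterion | Does it exclude this person? |
|---|---|
| Other interventional insomnia study | No: the therapy is ordinary care |
| Current trauma-focused PTSD therapy | No: CBT-I is not one of the therapies named |
| Benzodiazepines for sleep | No: concerns a drug |
| One-month stability | No: concerns medications only |
| ISI floor | No: the score is at or above 8 |

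A person who recently completed CBT-I and still has symptoms passes in the same way, because C.3 has no look-back or washout for behavioural therapy.

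**Step 2: look for an entry record.** The measures marked at Screen or Baseline cover diagnoses, symptoms, medications, medical problems and habits. None is described as recording behavioural insomnia treatment. The one measure named for that purpose starts at post-treatment.

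**Step 3: reproduce the plan's power figure (D.4).** The inputs are 150 participants (100 and 50), 3 time points, ICC 0.50, 10% attrition at each follow-up, and two-sided alpha 0.05.

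- Effective sample size (ESS) for n people with m observations each = n × m / (1 + (m − 1) × ICC).
- No attrition: 150 × 3 / 2 = 225, as stated.
- With attrition, 121.5 people give 3 observations, 13.5 give 2 and 15 give 1: 121.5 × 3/2 + 13.5 × 2/1.5 + 15 = 182.25 + 18 + 15 = 215.25, stated as 215.
- Detectable d at 80% power, with 215 split 1:2 into 71.67 and 143.33: (1.960 + 0.842) × √(1/71.67 + 1/143.33) = 2.802 × 0.1447 = 0.405. With the noncentral t it is 0.407. Both round to the stated 0.41.
- Power at exactly d = 0.41 is 0.81.

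The plan's figures reproduce, and the gap in C.3 does not depend on them.

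**Step 4: illustrate dilution.** The documents give no rate of outside CBT-I. Assume that a share p of both arms shows no contrast at all and that the true d in everyone else is 0.41. The diluted effect is 0.41 × (1 − p), and the sample size that keeps the same power grows by 1/(1 − p)².

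| p | Diluted d | Power at ESS 215 | Inflation | Participants needed |
|---|---|---|---|---|
| 0 | 0.41 | 0.81 | 1.00 | 150 |
| 5% | 0.39 | 0.77 | 1.11 | 167 |
| 10% | 0.37 | 0.72 | 1.23 | 186 |
| 20% | 0.33 | 0.62 | 1.56 | 235 |

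**The case against.** The case on the other side has real substance, and most of it limits the point.

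- **Insomnia treatment is not ignored outside research.** A reader might infer that C.3 restricts it only when it is part of a study. The benzodiazepine bullet and the medication-stability rule show otherwise, so the gap is confined to behavioural therapy. (The benzodiazepine bullet is phrased as a negative within an exclusion list, and that wording needs to be reconciled.)
- **Such therapy need not go unnoticed.** The telephone screen and the structured sleep interview precede randomisation, and their content is not reproduced. Therapy that continues into the trial may be picked up by the later measure or by the usual-care question. What stands is that no listed entry measure is described as recording it, and that without a criterion a positive answer would not exclude anyone.
- **Earlier and later treatment might still be separable.** The items and any start-date fields of the Insomnia Treatment Measure are not given, so the documents do not show that separation is impossible.
- **C.4.2 is not breached.** Its aim of no sleep advice attaches to the study's recorded check-in calls. Outside care is allowed by design in both arms.
- **Evidence that such people will present is thin.** The paper cited for the roll-out concerns veterans, and C.2 names no veterans' clinic.
- **The illustration is severe.** Recent completers must still have insomnia, and nothing shows that they would gain nothing from study CBT-I. The meta-analytic sleep-efficiency effect quoted in D.4, 0.54, would still be 0.54 × 0.8 = 0.43 at p = 20%, above the detectable 0.41.

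None of this supplies the missing criterion or the missing entry record.

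**Conclusion.** The gap is real and narrow. As written, C.3 admits people currently receiving, or just finished with, behavioural insomnia therapy in usual care, provided they still meet the diagnosis and the ISI floor. The plan describes no record of that therapy at entry.

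The likely consequence is attenuation of the Aim 1 contrast and no baseline variable to examine it. A reader might go further and infer confounding between the arms. That does not follow, because randomisation balances prior exposure on average. Nor do the documents support calling the trial underpowered on this account: the rate is unknown, 0.41 is a detectable rather than an expected effect, and D.4 itself says that the effect of CBT-I on cardiovascular risk is untested. The power values of 0.77, 0.72 and 0.62 hold only under an assumed share of 5%, 10% or 20% with zero contrast, and under the plan's own effective-sample-size method.

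The change is worth making because it is cheap and because an eligibility rule cannot be repaired at analysis.

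**What to change.** 1. In C.3, widen the bullet on other insomnia studies, for example: *Is currently receiving, or has recently completed, CBT-I or another structured behavioural insomnia therapy, whether in research or in usual care.* The sponsor should set and state the look-back period.
2. In the C.5 measures table, add the Insomnia Treatment Measure at Screen, so that the criterion can be applied and later treatment can be compared with a starting point.
3. If the sponsor prefers not to change eligibility, at least record prior and current behavioural insomnia treatment at entry for participants still to be enrolled.

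The cost is one existing questionnaire given once more and a few extra screen failures. The room for those failures depends on which screening figure holds: C.1 allows for as many as 500 people, whereas the timeline in section E totals 199 screened for 150 recruited.
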